#### **4.1 Inclusion Criteria**

- Medicare-certified
- All residents with Alzheimer's disease and related dementias.
- > 50 licensed beds
- >50% of residents are long-stay (>100 days in the facility)

#### **4.2 Exclusion Criteria**

- Patients currently enrolled in hospice at the start of the intervention period
- Problematic or unstable nursing homes
- Defined by corporate leadership prior to randomization

#### **4.3 Study Enrollment Procedures**

- Enrollment is occurring at the facility level; individual patients are not being enrolled.

### **5 STUDY INTERVENTIONS**

#### **5.1 Interventions, Administration, and Duration**

Following randomization, the ACP Specialist program will be rolled out to the intervention buildings. All communications will be tailored to fit the corporate branding style of Signature HealthCARE and Miller's Health Systems. Communications about the ACP Specialist Program with individual facilities will be delivered by the Corporate Implementation Champion and the designated ACP Specialists, with, at minimum, monthly meetings with the project team to discuss issues and any unmet needs. At the conclusion of the pragmatic cluster RCT, we will merge our data and analyze to measure

our primary and secondary outcomes.

## **6 STUDY PROCEDURES**

### **6.1 Description of Evaluations**

#### 6.1.1. Enrollment, Baseline, and/or Randomization

Nursing home Eligibility: All Medicare-certified nursing homes are eligible at Signature HealthCARE and Miller's Health Systems.

Nursing home Recruitment & Characteristics:

The ACP Specialist Program will be rolled out as a corporate initiative and nursing home Executive Directors will be requested to participate in the initiative by nursing home corporate leadership. It is anticipated all nursing home Executive Directors who are approached will agree to participate.

Nursing home corporate partners each provided data about key nursing home characteristics. At the time of randomization Signature HealthCARE owns 109 nursing homes in 8 states, with a total of 8,811 beds; 43% are rural. Miller's Health Systems owns 33 nursing homes, all in Indiana with 3,066 beds; 55% are rural. The mix of rural and urban facilities will provide a rich environment for this pragmatic trial. Self-reported 30-day hospital readmission rates for 2016 range from 13% for Miller's Health Systems and 17% for Signature HealthCARE nursing homes.

Random Assignment: Nursing homes will be sorted into groups that are comparable on hospital transfer rates. Eligible facilities who agree to participate in the trial will be stratified at two levels: corporate ownership (Signature HealthCARE and Miller's Health Systems) & average number of hospital transfers per 1000 person-days alive using 2017 MDS data. Facilities will be grouped into low versus high hospitalization rates, using the median rate for the nursing home system as the threshold value for dichotomization. Facilities will be randomized to the intervention or control within each strata at a 1-to-1 ratio. Specifically, randomization will occur at the facility level, meaning that all patients not currently on hospice at the start of the intervention period in the intervention buildings are eligible for inclusion in the trial. The intervention focuses on patients with ADRD, but other residents of intervention facilities are not excluded. Following random assignment, we will use all available facility and patient-level data to test the balance of the intervention and control arms.

## **7 SAFETY ASSESSMENTS**

IRB has determined this study to be minimal risk.

Although this study includes a vulnerable population of patients with cognitive impairment, it is anticipated that this study will be determined to represent no more than minimal risk to patients and family caregivers. All nursing homes are required to offer ACP to patients and family caregivers as part of routine care. This requirement is inclusive of patients with cognitive impairment or ADRD. Therefore, the ACP Specialist Program is consistent with the standard of care and the risk of harm is no greater than those ordinarily encountered in the daily life of a nursing home patient or family caregiver who may be offered the opportunity to engage in ACP by nursing home staff.

According to 45 CFR 46.102 (OHRP 2017), research is considered to pose minimal risk if the likelihood and degree of harm or discomfort anticipated from the research is no greater than that ordinarily encountered during daily life.

## 7.1 Adverse Events and Serious Adverse Events

An **adverse event (AE)** is generally defined as any unfavorable and unintended diagnosis, symptom, sign (including an abnormal laboratory finding), syndrome or disease which either occurs during the study, having been absent at baseline, or if present at baseline, appears to worsen.

A **serious adverse event (SAE)** is generally defined as any untoward medical occurrence that results in death, is life threatening, requires inpatient hospitalization or prolongation of existing hospitalization, results in persistent or significant disability/incapacity, or is a congenital anomaly.

The potential serious negative reaction (SNR) that could occur during this trial is serious patient or family caregiver distress when engaging in ACP with the ACP Specialist. Based on our experience and results from other research studies, we anticipate that this will be rare. Serious distress could be demonstrated by negative reactions such as anger, uncontrolled crying, or early termination of an ACP discussion with the Specialist. The nature of these discussions is sensitive and personal, thus expressions of emotion, including tears, is expected and would not be considered a SNR. Training of the ACP Specialist will include emphasis on the importance of asking permission to begin an ACP conversation and respecting patient and family refusals. It will also include provision of emotional support and empathic statements during discussions. ACP Specialist training will include recognition of SNRs and instruction. In the R33 phase, staff will be instructed to report any negative reactions immediately to the Executive Director and the nursing home Corporate Implementation Champion. Together, these health care providers will evaluate the severity of the event and, if deemed serious, will report the SNR to the research team project manager via email or fax within 24 hours of the event. The project manager will report the SNR to both co-PIs via email or telephone immediately upon becoming aware of the event and will also notify the TBN Data and Safety Monitoring Board (DSMB) Chair in writing (email and hard copy) within 48 hours. The Co-PIs will take ultimate responsibility for ensuring the DSMB chair is informed in a timely manner. Follow-up includes checking in with the patient or family caregiver within 6 to 24 hours of the initial SNR to assess whether further intervention is needed to mitigate the SNR. If necessary, the patient or family caregiver should be referred for follow-up (e.g., referring family caregiver to primary care provider or community mental health facility).

We do not believe any potential consequences of APPROACHES would be considered serious adverse events (SAEs). We do not believe that death should be considered an SAE for this trial as: 1) death is often not unexpected in this nursing home population with ADRD; 2) death is not an adverse outcome for patients and families with goals of comfort or palliation if those goals are met; and 3) it is not known whether or not

aggressive care provided at the hospital results in lower mortality compared with conservative care in the nursing home.

In this pragmatic trial, we will work closely with the nursing home corporate partners deploying the intervention in order to monitor the overall safety of patients in the project, minimize any risk associated with the research, and protect confidentiality. After the initiation of the R33, the nursing home Corporate Implementation Champions and nursing home Corporate Data Experts from each of the 2 nursing home partners will participate in monthly meetings to discuss project implementation and address questions, problems, or concerns that might arise, including data safety and risk to patients.

Co-PIs [name] and [name] will continue to actively monitor for any results of other new research studies or regulatory policies that may have an impact on APPROACHES. Further, we will request the DSMB members to monitor for any external scientific or therapeutic developments that could impact the ethics of the trial or safety of participants

## **7.2 Safety Monitoring**

The Co-PI [name] will be responsible for executing the DSMP in her role as the lead for the Regulatory and Operations Workgroup. Co-PI [name], the project manager, data manager, information technology (IT) support person, and the IT representatives for each of the two partner institutions will all participate in the Regulatory and Operations Workgroup. This workgroup will also be responsible for obtaining appropriate agreements for nursing home health system partners, including Memoranda of Understanding (MOU) and Data Use Agreements (DUA) prior to any data transfer. This workgroup has oversight of submission of CMS data requests, that must include all data security precautions, as well as submission of the protocol to the Indiana University Indianapolis (IUI) Institutional Review Board (IRB) for review and approval. The Regulatory and Operations workgroup will also support the coordination of DSMB. All study personnel, including PIs, Co-Is, consultant, project manager, and nursing home Corporate Implementation Champions will complete online education in the Protection of Human Research Practice and complete Conflict of Interest Forms. Our DSMP will be included as part of the research protocol and submitted to the IUI IRB.

### Frequency of Data and Safety Monitoring.

During the intervention phase of the R33 trial, nursing home Corporate Implementation Champions will be charged with asking nursing home based ACP Specialists about any adverse events and unanticipated problems that may have occurred in the course of their role. The nursing home Corporate Implementation Champions will meet at least monthly with the project team during the intervention phase. Any adverse events and unanticipated problems requiring immediate action will be discussed immediately with either of the PIs to determine necessary corrective action. Problems not requiring immediate actions will be addressed during monthly research team meeting and at quarterly DSMB meetings. Outcome of adverse events and unanticipated problems will be periodically reported to the IRB and the NIH.

### Content of Data and Safety Monitoring Report

A Data and Safety Monitoring Report will be prepared once a year and will include status, participant descriptive information, safety information, and fidelity monitoring.

#### Data and Safety Monitoring Board Membership

DSMB membership will include experts or representatives of the field with relevant clinical expertise, clinical trials methodology, and biostatistics. The members will be selected by the National Institute on Aging (NIA) program officer in consultation with the Co-PIs.

#### Conflict of Interests

Members of the DSMB shall have no direct involvement with the study investigators or nursing home corporate partners. Each DSMB member will sign the IU Conflict of Interest Statement, which include current affiliations and any other relationships that could be perceived as a conflict of interest related to the study.

#### Protection of Confidentiality

Data will be presented in a blinded manner with no participant or nursing home identifiers. All materials, discussions, and proceedings of the DSMB will be completely confidential and DSMB members are expected to maintain confidentiality.

#### DSMB Responsibilities

The DSMB will be formed in consultation with the NIA program officer and will include 2-3 external members. According to NIA guidance, the Chair will be selected by the NIA. The DSMB Chair will serve as the safety officer for the project and will be responsible for running meetings. The DSMB will be charged with monitoring patient safety, data quality and overall performance of the study. Responsibilities will include review of the research protocol, with a focus on protecting patient confidentiality and the plan for data and safety monitoring. Review of performance will include progress towards milestones, evaluation of recruitment, assessment of any serious negative reactions, and identification of issues around data storage or quality. The DSMB will also advise the NIA on the readiness of the trial to initiate recruitment, progress of the trial, and review of study performance including making recommendations and/or assisting in the resolution of problems identified by the Co-PIs. The DSMB will report to the NIA on the safety and progress of the trial as well as commenting on any problems with study conduct, enrollment, sample size, and/or data collection. All adverse events and unanticipated problems occurring during the course of the study will be collected, documented, and reported to the PIs and the DSMB Chair. These will be reported to NIA Project Officer and IRB quarterly. The PIs will meet with the study team staff weekly and at least one of the Co-PIs will be available at all times via email or phone. Serious adverse events potentially related to the intervention will be reported to both the Chair of the DSMB and to the NIA Project Officer within 24 hours of either PI learning of the issue. The DSMB Chair will determine if an additional meeting of the DSMB is needed and convene.

## 8 **INTERVENTION DISCONTINUATION**

### Adverse Event and Serious Adverse Event Collection and Reporting.

The potential *adverse event (AE)* that could occur during this trial is significant distress by patients or family members in the intervention NHs. Such events may be the manifestation of a very negative emotional reaction during a facilitated ACP discussion including uncontrolled crying or complaining to facility leadership. Due to the sensitive nature of the material, tearing up, crying, expressions of emotion, or early termination of the conversation by the proxy can be expected during advance care planning and are not deemed to be adverse events. The risk of potential distress caused by exposure to the ACP Specialist Program is no greater than the risk of distress from experiencing these conversations in routine clinical care.

Training of the ACP Specialist will include emphasis on the importance of asking permission to begin an ACP conversation and respecting patient and family refusals. It will also include provision of emotional support and empathic statements during discussions. ACP Specialist training will include recognition of AEs and instructions. In the R33 phase, staff will be instructed to report any negative reactions immediately to the Executive Director and the nursing home Corporate Implementation Champion. Instructions are provided to the ACP Specialists and Corporate Implementation Champions about what constitutes an adverse event. In the event of an AE, ACP Specialists will report the event to his/her immediate supervisor, who will report it to the Corporate Implementation Specialist. Together, these professionals will determine the severity of the event and if it is a true AE related to the ACP Specialist Program. If deemed necessary, the Corporate Implementation Champion will notify the research project staff within 48 hours of the event.

The project manager will report the AE to both co-PIs via email or telephone immediately upon becoming aware of the event and will also notify the TBN Data and Safety Monitoring Board (DSMB) Chair in writing (email and hard copy) within 48 hours. The Co-PIs will take ultimate responsibility for ensuring the DSMB chair is informed in a timely manner. Follow-up includes checking in with the patient or family caregiver within 6 to 24 hours of the initial AE to assess whether further intervention is needed to mitigate the AE. If necessary, the patient or family caregiver should be referred for follow-up (e.g., referring family caregiver to primary care provider or community mental health facility). A summary of any AEs will be reported quarterly to the NIA program officer and the IRB.

We do not believe any potential consequences of APPROACHES would be considered serious adverse events (SAEs). We do not believe that death should be considered an SAE for this trial as: 1) death is often not unexpected in this nursing home population with ADRD; 2) death is not an adverse outcome for patients and families with goals of comfort or palliation if those goals are met; and 3) it is not known whether or not aggressive care provided at the hospital results in lower mortality compared with conservative care in the nursing home.

In this pragmatic trial, we will work closely with the nursing home corporate partners deploying the intervention in order to monitor the overall safety of patients in the project, minimize any risk associated with the research, and protect confidentiality. After the initiation of the R33, the nursing home Corporate Implementation Champions and nursing home Corporate Data Experts from each of the 2 nursing home partners will participate in monthly meetings to discuss project implementation and address questions, problems, or concerns that might arise, including data safety and risk to patients.

Co-PIs [name] and [name] will continue to actively monitor for any results of other new research studies or regulatory policies that may have an impact on APPROACHES. Further, we will request the DSMB members to monitor for any external scientific or therapeutic developments that could impact the ethics of the trial or safety of participants.

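### Sections 8 and 7.1 let facility and corporate staff screen suspected adverse events before the research team is told, which conflicts with section 7.2's commitment that all of them reach the PIs and the DSMB Chair

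*Combined protocol and SAP*

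**What the plan says.** Section 8 (Adverse Event and Serious Adverse Event Collection and Reporting) sets the route for a distress event in an intervention home. Staff are to bring negative reactions at once to the Executive Director and the Corporate Implementation Champion. The formal chain is then: "ACP Specialists will report the event to his/her immediate supervisor, who will report it to the Corporate Implementation Specialist". Those staff jointly "determine the severity of the event and if it is a true AE related to the ACP Specialist Program". The next step is conditional: "If deemed necessary, the Corporate Implementation Champion will notify the research project staff within 48 hours of the event". The project manager informs the co-PIs and the DSMB Chair, but only from the moment the project manager learns of the event.

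Section 7.1 has a parallel route for serious negative reactions. The Executive Director and the Champion assess severity, and the project manager hears, within 24 hours, of those they judge serious.

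Section 7.2 (DSMB Responsibilities) sets no condition: "All adverse events and unanticipated problems occurring during the course of the study will be collected, documented, and reported to the PIs", with the DSMB Chair as second recipient. Under Frequency of Data and Safety Monitoring, the Champions are also charged with "asking nursing home based ACP Specialists about any adverse events and unanticipated problems". Matters needing immediate action go straight to a PI. The rest go to monthly team meetings and quarterly DSMB meetings.

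**The concern.** A facility that follows section 8 exactly can hold back an event that section 7.2 says must reach the PIs and the DSMB Chair. The people who decide are facility and corporate staff, and they decide before anyone on the research team knows of the event.

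This matters because patient or family distress is the only potential harm the plan names. Distress is not among the outcomes drawn from the EHR, MDS or Medicare claims, and section 9.3 rules out an interim analysis. These reports are therefore the main signal of harm while the trial runs. If they are screened before they arrive, a low count has two explanations, few events or few events forwarded, and the DSMB cannot tell them apart.

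**Working it through.** The plan gives no figure to reproduce on this point, so the check is a comparison of the reporting passages.

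1. **Order of steps in section 8.** Event, ACP Specialist, supervisor, corporate lead, judgement of severity and relatedness, judgement of necessity, project staff, then co-PIs and DSMB Chair. Both judgements come before the first contact with the research team. The duty to notify the co-PIs and the Chair lies after them.

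2. **Conditions in section 7.2.** There are none on adverse events and unanticipated problems. The same subsection does limit by relatedness when it turns to serious adverse events, where the 24-hour rule covers those potentially related to the intervention. The broader sentence has no such limit.

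3. **Definition in section 7.1.** An adverse event is defined by appearing or worsening during the study. Relatedness to the programme is not part of the definition. An event judged unrelated locally is still an adverse event under section 7.1, and section 7.2 would send it on. Section 8 may stop it.

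4. **Section 7.1's own screen.** Serious negative reactions pass a local judgement of seriousness before the project manager is told. Amending section 8 alone would leave that conflict in place.

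5. **Other routes.** The Champion's questioning under section 7.2 covers any adverse event and is not tied to the relatedness test. The monthly meetings described in sections 7.1 and 8 cover risk to patients. But the Champion asks the questions, and Champions and corporate data experts bring the facilities' information to the meetings. An event already set aside in the corporate chain resurfaces only if someone in that chain raises it.

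6. **Record of events not forwarded.** No section requires a log, or a review by anyone outside the chain.

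7. **Size.** A loss estimate needs the number of discussions, the rate of significant distress and the share screened out. The documents give neither of the last two. Even the first is loose. With 142 / 2 = 71 intervention homes, 10 assigned patients a month (section 13) over 18 months gives at most 71 × 10 × 18 = 12,780 planned approaches. Taking instead the 50 residents per facility assumed in section 9.2, approached once each, gives 71 × 50 = 3,550. These differ by a factor of 12,780 / 3,550 = 3.6 before any rate is assumed.

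**The case against.** The strongest reply is that first triage by the site is a legitimate choice in a trial the IRB has classed as minimal risk, and that section 7.2's sentence may mean all events already accepted as adverse events. Part of this stands. Section 8 treats tears and similar expressions as expected, and nobody needs those forwarded. But the narrow reading is not written anywhere, section 7.1's definition points the other way, and the further condition of necessity has no counterpart in section 7.2.

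Some stronger readings are tempting, and the documents do not support them:

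- *Screened-out events never leave the corporation.* The Champion's questions and the monthly meetings could bring them out. Loss is possible but not shown.
- *Section 5.1 shows that the assessors deliver the programme.* The words "will be delivered by the Corporate Implementation Champion and the designated ACP Specialists" refer to communications about the programme with facilities, not to delivery or to causality. Section 7.2 also counts Champions among study personnel who complete human-research education and conflict-of-interest forms. What remains is structural: the assessors are facility and corporate staff, and section 14 makes corporate partners eligible for authorship. Neither fact shows bias.
- *Complaints to facility leadership escape because only Specialists are questioned.* Section 8 already names the Executive Director as a recipient of negative reactions.
- *The consent waiver depends on a low adverse event count.* Section 11.2 rests it on minimal risk and the other regulatory criteria. Section 7 derives minimal risk from ACP already being required in routine care.

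**Conclusion.** The point holds as a conflict between safety-reporting passages. Sections 8 and 7.1 make reporting to the research team conditional on a local judgement, while section 7.2 promises all events without condition. The distress count reaching the PIs and the DSMB may therefore be incomplete. Its shortfall cannot be estimated, and any number of missed events would rest wholly on assumed rates.

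The conclusion assumes that the Corporate Implementation Specialist and the Corporate Implementation Champion in section 8 are one role, or at least both corporate roles. The text uses both titles without explanation. The conclusion does not assume that anyone would withhold a report.

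The effect is confined to safety reporting. Hospital transfers, hospice enrollment and death in hospital come from existing data sources and do not pass through this chain. The correction is worth making because it is cheap and this is the only harm being watched for, but it does not bear on the trial's main comparison.

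**What to change.** Reconcile sections 7.1 and 8 with section 7.2 by removing the local judgements of relatedness, severity and necessity as conditions for reporting. Possible text for both sections:

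> *Every suspected adverse event or serious negative reaction is sent to the project manager with the facility's opinion on severity and relatedness attached. Expected expressions of emotion, as listed in this section, are not reported. The Co-PIs record the classification, and the DSMB Chair receives all reports together with the facility's opinion.*

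The Co-PIs lead the programme, so their classification is not independent either. That is why the Chair should receive every report, not only those they classify as related.

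Three loose ends in the same passages need reconciling at the same time, and the sponsor must decide how. The time limit for telling the research team is 24 hours in section 7.1 and 48 hours in section 8. Early termination of a discussion is a possible sign of a serious negative reaction in section 7.1, but section 8 calls it expected when the proxy ends the conversation. The two corporate titles should become one. The new rule needs a single list of expected reactions to be workable.

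The cost is protocol wording, a line in the existing training, and somewhat more low-grade reports for the Co-PIs to classify and the Chair to read. No new staff or visits are needed.
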